10.3.8.1 Collection of Defect Information in Stage of Manufacture, Delivery and Storage

Provision of information from QA to Pharmacovigilance (PV):

- If QA determines that there is a significant quality issue in the defect information collected after shipment of the IPs, QA will send it to PV. When it is judged as a significant quality issue, the impact on the participant is also evaluated by QA, therefore PV evaluates the provided information and reports it to the Pharmaceutical and Medical Devices Agency (PMDA).

Provision of information from the PV department to the quality assurance department:

- When the defect information is reported to PV from the investigational sites, PV will send it to QA. If QA obtains the follow-up information, QA will send it to PV and PV will submit the additional report to PMDA.

10.3.9 Urgent Safety Measures

An urgent safety measure (USM) is an intervention that is not defined by the protocol and can be put in place with immediate effect without needing to gain prior approval by the sponsor, relevant competent authorities, IRB/IEC, where applicable, in order to protect participants from any immediate hazard to their health and/or safety. Either the investigator or the sponsor can initiate a USM. The cause of a USM can be safety-, product- or procedure-related.

When the sponsor receives a safety issue from any source (either Japan or worldwide) that requires a USM to be implemented, then the sponsor will report that safety information to all study sites in Japan and the rest of world (within 24 hours of awareness).

10.3.10 Reporting Urgent Safety Measures

In the event of a potential USM, the investigator must contact the study physician and/or an Astellas team member (within 24 hours of awareness). Full details of the potential USM are to be recorded in the participant's medical records. The sponsor may request additional information related to the event to support their evaluation.

If the event is confirmed to be a USM, the sponsor will take appropriate action to ensure the safety and welfare of the participants. These actions may include but are not limited to a change in study procedures or study treatment, halting further enrollment in the study, or stopping the study in its entirety. The sponsor or sponsor's designee will notify the relevant competent authorities and concerned ethics committee within the timelines required per current local regulations, and will inform the investigators, as required. When required, investigators must notify their IRB/IEC within timelines set by regional regulations.

10.4 Appendix 4: Liver Safety Monitoring and Assessment

The purpose of this appendix is to provide guidance for the monitoring of drug-induced liver injury during the course of the study. It should be noted that this section does not specify the end-of-study analyses of liver enzymes. The end-of-study liver enzymes analyses will be described in the SAP. Any participant enrolled in a study with active drug therapy and reveals an increase of serum aminotransferases (AT) to $> 3 \times$ ULN or bilirubin $> 2 \times$ ULN should undergo detailed testing for liver enzymes (including at least alkaline phosphatase [ALP], ALT, AST and TBL). Testing should be repeated within 72 hours of notification of the test results. For studies for which a central laboratory is used, alerts will be generated by the central laboratory regarding moderate and severe liver abnormality to inform the investigator and study team. Participants should be asked if they have any symptoms suggestive of hepatobiliary dysfunction.

Definition of Liver Abnormalities

Confirmed abnormalities will be characterized as moderate and severe where ULN is as shown below.

Table 12 Moderate and Severe Liver Abnormalities

	ALT or AST		TBL
Moderate	$> 3 \times$ ULN	or	$> 2 \times$ ULN
Severe	$> 3 \times$ ULN	and†	$> 2 \times$ ULN

ALT: alanine aminotransferase; AST: aspartate aminotransferase; TBL: total bilirubin; ULN: upper limit of normal

†Samples taken simultaneously or within maximum 24 hours.

In addition, the participant should be considered to have severe hepatic abnormalities for any of the following:

- ALT or AST $> 8 \times$ ULN
- ALT or AST $> 5 \times$ ULN for more than 2 weeks.
- ALT or AST $> 3 \times$ ULN and† TBL $> 2 \times$ ULN or international normalized ratio (INR) > 1.5 (if INR testing is applicable/evaluated)
- ALT or AST $> 5 \times$ ULN and† (TBL $> 2 \times$ ULN in participants with liver metastases)
- ALT or AST $> 3 \times$ ULN with the appearance of fatigue, nausea, vomiting, right upper quadrant pain or tenderness, fever, rash and/or eosinophilia ($> 5\%$)

† Samples taken simultaneously or within a maximum of 24 hours.

The investigator may determine that abnormal liver function results, other than as described above, may qualify as moderate or severe abnormalities and require additional monitoring and follow-up.

Follow-up Procedures

Confirmed moderate and severe abnormalities in hepatic functions should be thoroughly characterized by obtaining appropriate expert consultations, detailed pertinent history, physical examination and clinical laboratory tests. The study site personnel are to complete

the liver abnormality case report form (LA-CRF). Participants with confirmed abnormal liver function testing should be followed as described below.

Confirmed moderately abnormal liver function tests should be repeated 2 to 3 times weekly, and then weekly or less if abnormalities stabilize or the IP has been discontinued and the participant is asymptomatic.

Severe hepatic liver function abnormalities as defined above, in the absence of another etiology, may be considered an important medical event and may be reported as an SAE. The sponsor should be contacted and informed of all participants for whom severe hepatic liver function abnormalities possibly attributable to IP are observed.

To further assess abnormal hepatic laboratory findings, the investigator is expected to:

- Obtain a more detailed history of symptoms and prior or concurrent diseases. Symptoms and new-onset diseases are to be recorded as “AEs” within the eCRF. Illnesses and conditions such as hypotensive events, and decompensated cardiac disease that may lead to secondary liver abnormalities should be noted. Nonalcoholic steatohepatitis is seen in obese hyperlipoproteinemic and/or diabetic participants, and may be associated with fluctuating AT levels. The investigator should ensure that the medical history form captures any illness that predates study enrollment that may be relevant in assessing hepatic function.
- Obtain a history of concomitant drug use (including nonprescription medication, complementary and alternative medications), alcohol use, recreational drug use and special diets. Medications are to be entered in the eCRF. Information on alcohol, other substance use and diet should be entered on the LA-CRF or an appropriate document.
- Obtain a history of exposure to environmental chemical agents.
- Based on the participant’s history, other testing may be appropriate including:
 - Acute viral hepatitis (A, B, C, D, E or other infectious agents)
 - Ultrasound or other imaging to assess biliary tract disease
 - Other clinical laboratory tests, including INR and direct bilirubin
- Consider gastroenterology or hepatology consultations.
- Submit results for any additional testing and possible etiology on the LA-CRF or an appropriate document.

Study Treatment Discontinuation

In the absence of an explanation for increased liver function tests, such as viral hepatitis, preexisting or acute liver disease, or exposure to other agents associated with liver injury, the participant may be discontinued from study treatment. The investigator may determine that it is not in the participant’s best interest to continue study treatment. Discontinuation of study treatment should be considered if:

- ALT or AST $> 8 \times$ ULN
- ALT or AST $> 5 \times$ ULN for more than 2 weeks
- ALT or AST $> 3 \times$ ULN and† TBL $> 2 \times$ ULN or INR > 1.5 (if INR testing is applicable/evaluated)

- ALT or AST $> 5 \times$ ULN and† (TBL $> 2 \times$ ULN in participants with liver metastases)
- ALT or AST $> 3 \times$ ULN with the appearance of fatigue, nausea, vomiting, right upper quadrant pain or tenderness, fever, rash and/or eosinophilia ($> 5\%$)

†Samples taken simultaneously or within a maximum of 24 hours.

In addition, if close monitoring for a participant with moderate or severe hepatic laboratory tests is not possible, study treatment should be discontinued.

Hy's Law definition: Drug-induced jaundice caused by hepatocellular injury, without a significant obstructive component, has a high rate of bad outcomes, from 10% to 50% mortality (or transplant).

The 2 "requirements" for Hy's Law are:

1. Evidence that a drug can cause hepatocellular-type injury, generally shown by an increase in AT elevations $> 3 \times$ ULN ("2 \times ULN elevations are too common in treated and untreated participants to be discriminating").
2. Cases of increased TBL (at least 2 \times ULN) with concurrent AT elevations at least 3 \times ULN and no evidence of intra- or extra-hepatic bilirubin obstruction (elevated ALP) or Gilbert's syndrome [Temple, 2006].

FDA Guidance for Industry titled, "Drug-induced Liver Injury: Premarketing Clinical Evaluation" issued by the FDA on July 2009:

1. The drug causes hepatocellular injury, generally shown by a higher incidence of 3-fold or greater elevations above the ULN of ALT or AST than the (nonhepatotoxic) control drug or placebo.
2. Among participants showing such AT elevations, often with ATs much greater than 3 \times ULN, one or more also show elevation of serum TBL to $> 2 \times$ ULN, without initial findings of cholestasis (elevated serum ALP).
3. No other reason can be found to explain the combination of increased AT and TBL, such as viral hepatitis A, B, or C; preexisting or acute liver disease; or another drug capable of causing the observed injury.

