Kidney	Increased serum creatinine. Basophilic tubules and infiltration of mononuclear cells	Standard monitoring of kidney function parameters (creatinine, blood urea nitrogen) and urinalysis
Spleen	Increased weight, apoptosis in lymphoid follicles, emboli, lymphoid follicular hyperplasia	Standard laboratory assessment of hematology
General	Immune-Mediated Adverse Reaction, Cytokine-release syndrome – Not observed non-clinically	Close monitoring of participant's signs or symptoms; Chemokine/Cytokine panel and tryptase level.
	Infusion-Related Reaction – Not observed non-clinically	Close monitoring of participant's signs or symptoms; Chemokine/Cytokine panel and tryptase level.
	Immunotoxicity directed against non-target toxicity (testis and placenta) - Risk cannot be ruled out based on nonclinical studies. However, as NY-ESO-1 is only expressed in immune privileged organs, the risk is considered low [Raza et al, 2020].	Close monitoring of participant's signs or symptoms; Testosterone testing in male participants
	Allergic Reactions and Anaphylaxis – Not observed non-clinically	Close monitoring of participant's signs or symptoms; Chemokine/Cytokine panel and tryptase level.

ALT: alanine aminotransferase; AST: aspartate aminotransferase; RBC: red blood cells; WBC: white blood cell

- **Liver Toxicity:** Close monitoring of liver function and toxicities is required during clinical studies. The liver is a target organ of toxicity for ASP0739, which is related to the activation of the innate immune system by α -GalCer. The hepatic findings in mice included increased liver weight, elevated aspartate aminotransferase (AST) and alanine aminotransferase (ALT) levels, emboli, hepatocyte focal necrosis, mixed inflammatory cell infiltration, microgranuloma, granulomatous inflammation, mononuclear cell aggregation and pigment laden macrophage infiltration. The hepatic findings of increased AST and ALT 1 day after administration of ASP0739 were completely reversed following a 28-day recovery period.
- **Hematology:** The standard assessment of hematology is recommended in clinical studies. A dose-related decrease in platelet count was seen 1 day after the first and second dose. Platelet counts were increased above baseline 7 days after the first and second dose and recovered to normal physiological ranges by day 28.

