10.3.1.2 Potential Cases of Drug-induced Liver Injury

Refer to [Section 10.4 Appendix 4: Liver Safety Monitoring and Assessment] for detailed instructions on drug induced liver injury. Abnormal values in AST and/or ALT concurrent or with abnormal elevations in TBL that meet the criteria outlined in [Section 10.4 Appendix 4: Liver Safety Monitoring and Assessment], in the absence of other causes of liver injury, are considered potential cases of drug-induced liver injury (potential Hy's Law cases) and are always to be considered important medical events and reported per [Section 10.3.6 Reporting Procedures for Serious Adverse Events].

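### For liver enzyme elevations with raised bilirubin and no other cause, Section 10.3.1.2 makes SAE reporting mandatory within 24 hours, while Appendix 4 makes it optional with no time limit

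*Protocol*

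**What the plan says.** Two parts of the protocol set the reporting status of a severe liver abnormality.

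- **Section 10.3.1.2** covers this case: "Abnormal values in AST and/or ALT concurrent or with abnormal elevations in TBL that meet the criteria outlined in" Appendix 4, "in the absence of other causes of liver injury". These are potential Hy's Law cases. They "are always to be considered important medical events and reported per" Section 10.3.6, which requires an SAE worksheet within 24 hours of awareness.
- **Appendix 4 (Section 10.4)** defines severity in "Table 12 Moderate and Severe Liver Abnormalities". Severe there means ALT or AST above 3 × ULN and TBL above 2 × ULN, in samples taken together or within 24 hours. A further list follows: "In addition, the participant should be considered to have severe hepatic abnormalities for any of the following". Under Follow-up Procedures, severe abnormalities as defined there, "in the absence of another etiology, may be considered an important medical event and may be reported as an SAE". The next sentence reads: "The sponsor should be contacted and informed of all participants for whom severe hepatic liver function abnormalities possibly attributable to IP are observed". It names no deadline and no SAE form.

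The protocol's risk assessment (Section 2.3.1.1) states: "The liver is a target organ of toxicity for ASP0739".

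**The concern.** The same laboratory combination, under the same no-other-cause condition, carries a duty to report in one place and an option in the other. Section 10.3.1.2 sends the reader to Appendix 4 for detailed instructions, which is where the weaker wording stands. A site working from Appendix 4 could record a potential Hy's Law case as a non-serious AE and still comply with that page.

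At stake is whether the site's SAE report is made, and made within 24 hours. Under Section 10.3.6 the sponsor's evaluation for expedited reporting is an evaluation of the SAE. For an organ that the protocol itself names as a target of toxicity, the reporting rule should not differ between two pages.

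**Working it through.** The plan states no figure on this point, so there is nothing to recompute. The check compares the two rules by type of case, then looks for text that resolves the conflict, then traces what depends on the classification.

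**1. The rules side by side, for a case with no other cause**

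| Case | Section 10.3.1.2 | Appendix 4 | Conflict? |
|---|---|---|---|
| (a) ALT or AST > 3 × ULN with TBL > 2 × ULN | always; report within 24 hours via 10.3.6 | may be; no deadline | yes |
| (b) ALT or AST > 5 × ULN with TBL > 2 × ULN, liver metastases | always; report within 24 hours via 10.3.6 | may be; no deadline | yes |
| (c) ALT or AST > 8 × ULN; > 5 × ULN for more than 2 weeks; > 3 × ULN with INR > 1.5; > 3 × ULN with symptoms; all without raised TBL | not covered | may be | no |

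**2. Is there text that settles it?** Section 10.3.2 says that important medical events should usually be considered serious, which lies between the two rules and decides nothing. Appendix 4 contains no reference back to Section 10.3.1.2. No statement of precedence was found.

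**3. What depends on the site's classification?**

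- *24-hour worksheet and expedited review (Section 10.3.6).* Both depend on it, because they apply to SAEs.
- *Serious TEAE tables (SAP 6.5.2).* They depend on it unless the sponsor upgrades the event from its Always Serious list. The documents neither reproduce that list nor say when the upgrade is made.
- *Events 31 to 90 days after last treatment.* SAP 6.5.2 summarizes AEs to 30 days and SAEs to 90 days, and Protocol Table 3 collects both at the 30-, 60- and 90-day visits. A case on day 45, for example, falls inside the SAE window (45 ≤ 90) and outside the AE window (45 > 30). It is summarized if reported as an SAE and can drop out of the summaries if not. This rests on the opening paragraph of SAP 6.5.2; most of the tables itemized below it are restricted to TEAEs, which end at 30 days. AE data are listed in any case.
- *DLT review.* It does not depend on it. Protocol Section 4.1 lists AST or ALT > 3 × ULN with TBL > 2 × ULN as a DLT, confirmed by the DESC. This route is limited to IP-related events in the first 28 days of the escalation and combination lead-in cohorts.
- *Liver table (SAP 6.5.4.1).* It does not depend on it, because it is built from laboratory values. It requires both values in the same sample, whereas Table 12 accepts samples up to 24 hours apart, so its combination row is slightly narrower than the protocol's definition.

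**The case against.** The strongest reply is that the two texts can both be obeyed. Permission to report does not forbid reporting, so a site that follows Section 10.3.1.2 also complies with Appendix 4. Section 10.3.1.2 is the specific, mandatory rule. Section 7.3 sends sites to Section 10.3 for SAE procedures, and Appendix 4 describes its purpose as guidance on monitoring. On the usual reading the specific duty governs, and breaching it is not excused by the wording elsewhere. That a site would rely on Appendix 4 alone is a supposition.

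This stands as an account of how a careful reader should resolve the texts. It does not remove the defect: the protocol never says so, and Section 10.3.1.2 itself directs sites to the page with the optional wording.

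A reader might go further and infer that the safety committee would not see such a case, or that the liver signal would be lost from the analysis. The documents do not support that. Beyond the DLT and laboratory routes, the DESC considers all available safety findings (Sections 4.1 and 10.1.5.2). Sites complete a liver abnormality case report form for confirmed moderate and severe cases, and the sponsor should be informed of severe cases possibly attributable to the product (Appendix 4). An event may also be serious on other grounds, such as hospitalization.

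Nor is every severe liver category in conflict: for group (c), Appendix 4 is the only rule and its discretion is coherent.

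**Conclusion.** The inconsistency is real and confined to groups (a) and (b). For those cases the obligation moves from a mandatory report within 24 hours to an optional one with no stated limit. Three things depend on it: the site's SAE report, the expedited-reporting review that starts from it, and the site-reported serious classification, including the 31-to-90-day window.

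This has no useful size as a rate. One reclassified participant moves a serious-event percentage by 1/3 = 33, 1/6 = 17 or 1/12 = 8 points in cohorts of 3, 6 or 12, but that holds for any single event and says nothing about how likely this one is. The documents report no such case: at 06 May 2022 the protocol describes 4 treated participants with no DLTs or safety concerns.

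The practical effect assumes that a site treats Appendix 4 as governing and that the case is not serious on other grounds. For the serious-event tables it also assumes that the sponsor has not upgraded the event. It is a drafting conflict that should be removed.

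**What to change.** Reconcile the two passages. In the Follow-up Procedures of Appendix 4, take ALT/AST elevations with TBL elevation meeting the severe criteria and without another cause out of the optional sentence. State by cross-reference that Section 10.3.1.2 applies to them: always an important medical event, reported under Section 10.3.6. Leave the optional wording for the other severe categories.

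The SAP says that the study terminated early, without the planned combination treatment, so an amendment may not be made. In that case, before database lock, identify every participant whose laboratory values meet these combinations, using the 24-hour window of Table 12 and not only the same-sample rule of SAP 6.5.4.1. Check each one without another cause against the SAE records.

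The cost is one sentence and a cross-reference, or one short reconciliation listing. The downside is possibly a few more SAE reports.

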10.5 Appendix 5: List of Excluded Concomitant Medications

10.5.1 Concomitant Medications

The following list describes concomitant medications that are prohibited. This list should not be considered all inclusive. If there are concerns or questions about concomitant use of any drugs listed below, discussion with the medical monitor is strongly encouraged.

Drug Type	Generic Drug Name
Corticosteroids*	Dexamethasone Prednisone (Deltasone, Orasone, Predone, RAYOS, Sterapred, etc.)
Interferon/polyethylene-interferon	
Immunosuppressive Agents	Abatacept (Orencia, etc.) Adalimumab (Humira, etc.) Anajunra (Kineret, etc.) Azathioprine (Azasan, Imuran, etc.) Budesonide (Entocort EC, etc.) Certolizumab (Cimzia, etc.) Cyclosporine (Neoral, Sandimmune, SangCya, etc.) Etanercept (Enbrel, etc) Everolimus (Afinitor, Zortress, etc.) Golimumab (Simponi, etc.) Infliximab (Remicade, etc.) Ixekizumab (Taltz, etc.) Leflunomide (Arava, etc.) Mycophenolate (CellCept, Myfortic, etc.) Natalizumab (Tysabri, etc.) Prednisolone (Millipred, etc.) Rituximab (Rituxan, etc.) Secukinumab (Cosentyx, etc.) Sirolimus (Rapamune, etc.) Tocilizumab (Actemra, etc.) Tofacitinib (Xeljanz, etc.) Ustekinumab (Stelara, etc.) Vedolizumab (Entyvio, etc.)

*The use of high dose system corticosteroids are prohibited, with the exception of immune-related AEs.

10.5.2 Other Investigational Agents

Treatment with investigational agents other than ASP0739 or pembrolizumab is prohibited. If there are concerns or questions about concomitant use of these drugs, discussion with the co-chairs and protocol officer is strongly encouraged.

10.6 Appendix 6: Clinical Laboratory Assessments

Laboratory tests will be performed according to the schedule of assessments.

Table 13 Clinical Laboratory Tests

Panel/Assessments	Parameters to be Analyzed
Hematology	Hematocrit (Hct) Hemoglobin (Hgb) Mean corpuscular volume (MCV) Mean corpuscular hemoglobin (MCH) Mean corpuscular hemoglobin concentration (MCHC) Platelet count Red blood cell count (RBC) White blood cell count (WBC) White blood cell count differential
Chemistry	Sodium (Na) Potassium (K) Chloride (Cl) Bicarbonate (HCO ₃) or CO ₂ † Blood urea nitrogen (BUN) Creatinine (Cr) Glucose (Gl) Calcium (Ca) Phosphate (Pi) Magnesium (Mg) Albumin (Alb) Total protein (T Prot) Alkaline phosphatase (ALP) Lactate dehydrogenase (LDH) Creatine phosphokinase (CK) Liver function tests including: Bilirubin total (TBL) Alanine aminotransferase (ALT) Aspartate aminotransferase (AST)
Table continued on next page	

Panel/Assessments	Parameters to be Analyzed
Urinalysis	Color Appearance Specific gravity pH Bilirubin Blood Glucose Ketones Leukocyte esterase Nitrite Protein Urobilinogen
Urine/Serum Pregnancy Test*	hCG
Coagulation Profile (PT/INR, Fibrinogen)	Activated partial thromboplastin time (aPTT) International normalized ratio (INR) Prothrombin time (sec) (PT) Fibrinogen
Thyroid Panel (combination cohort only)	Triiodothyronine or free triiodothyronine Free thyroxine Thyroid stimulating hormone

eCRF: electronic case report form; hCG: human chorionic gonadotrophin; PT/INR: prothrombin time/international normalized ratio.

†If testing is not available, this test is not mandatory.

*Local results will be collected and entered into the eCRF.

